#### **3.8.3.2 Documenting Reasons for Discontinuation**

All subjects have the right to withdraw and the investigator or subinvestigator can discontinue a subject's participation in the trial at any time if medically necessary. In addition, subjects meeting the following criteria must be withdrawn from the trial. Only

one reason for discontinuation (the main reason) can be recorded in the source documents and CRF, along with the date of discontinuation.

- 1) Adverse event:
  - a) Death
  - b) Subject experiences exacerbation of symptoms of the underlying disease, and the investigator or subinvestigator judges that continued participation in the trial is inappropriate
  - c) Subject experiences a change to the manic state
  - d) Based on clinical symptoms, subject is considered to be at high risk of suicide in the opinion of the investigator or subinvestigator or has an MADRS score for Suicidal Thought (No. 10) of  $\geq 5$  or HAM-D suicide score (No. 11) of  $\geq 3$ , or those answering "Yes" to question 4 or 5 of C-SSRS.
  - e) Subject decides to discontinue because of annoyance or discomfort due to a nonserious AE which is not otherwise determined to be an undue hazard
  - f) Continuation of IMP would place the subject at undue risk as determined by the investigator or subinvestigator (eg, there is a safety concern possibly, probably, or likely related to IMP)
    - i) SAE
    - ii) Other safety concern or AE possibly, probably, or likely related to IMP
- 2) Subject's withdrawal of informed consent
  - a) Reasons unrelated to medical condition (issues regarding subject's convenience, such as a change of residence or other commitments: provide detail and review AE history with subject)
  - b) Withdrawal of informed consent (complete written withdrawal of consent form)
- 3) Marked noncompliance with the IMP regimen
  - a) Compliance rate of  $< 65\%$  during the interval between 2 consecutive scheduled visits
- 4) Protocol deviation
  - a) Subject is discovered to have not been in accord with inclusion/exclusion criteria
  - b) Subject has received any prohibited concomitant drugs or therapies, or is judged to be in need of such
  - c) Subject can no longer be administered antidepressant (SSRI or SNRI for rollover subjects and SSRI, SNRI, or mirtazapine for new subjects)
- 5) Lost to follow-up
- 6) Pregnancy (see Section 5.5 Pregnancy)
- 7) Termination of all or part of the trial by the sponsor
- 8) Discontinuation of the trial site by the sponsor
- 9) Lack of efficacy

- 10) Impossibility of protocol compliance or judgement by the investigator or subinvestigator that discontinuation is necessary for any reason other than the above

If the subject discontinues IMP due to an AE, the investigator, subinvestigator, or other trial personnel will make every effort to follow the event until the event is resolved or stabilized, or the subject is lost to follow up or has died. Follow-up procedures in [Section 3.8.3.1 Treatment Discontinuation](#) must be followed.

### **3.8.3.3 Withdrawal of Consent**

All subjects have the right to withdraw their consent from further participation in the trial at any time without prejudice. Subjects cannot withdraw consent for use of data already collected as part of the trial, but only for future participation. The investigator or subinvestigator can also discontinue a subject's participation in the trial at any time if medically necessary. Unless the subject provides their written withdrawal of consent or there is other written documentation by the investigator or subinvestigator confirming the subject's verbal intent to completely withdraw from the trial, subjects should be followed for all protocol-specified evaluations and assessments, if possible.

Complete withdrawal of consent requires refusal by a subject of ALL of the following methods of follow up (these methods of follow up will also be noted in the trial ICF):

- Participation in all follow-up procedures specified in the protocol (whether in-clinic, by telephone, or by an in-home visit).
- Participation in a subset of protocol specified follow-up procedures (by a frequency schedule and method, as agreed by subject and staff).
- Contact of the subject by trial personnel, even if only by telephone, to assess current medical condition, and obtain necessary medical or laboratory reports relevant to the trial's objectives.
- Contact of alternative person(s) who have been designated in source documents as being available to discuss the subject's medical condition, even if only by telephone, mail, or e-mail (eg, family, spouse, partner, legal representative, friend, neighbor, or physician).
- Access to medical information from alternative sources (eg, hospital/clinic medical records, referring doctor's notes, public records, dialysis, transplantation or vital registries, social media sources).

Withdrawal of consent is a critical trial event and therefore should be approached with the same degree of importance and care as is used in initially obtaining informed consent. The reasons of a subject for an intended withdrawal need to be completely understood, documented, and managed to protect the rights of the subject and the integrity of the trial. A subject may initially express their desire to discontinue IMP administration, which is not equivalent to a complete withdrawal of consent for further participation (see [Section](#)

3.8.3.1 Treatment Discontinuation). A subject may, however, indicate that further trial participation is creating a burden on their work or social schedule. Therefore, the investigator or subinvestigator should follow the procedures outlined in [Section 3.8.3.2 Documenting Reasons for Discontinuation](#) to determine if the subject can continue participation in the trial if modifications to his/her treatment and/or schedule of assessments can be accommodated. Only subjects who withdraw their permission for all of the above degrees of follow-up are considered to have completely withdrawn their consent to participate in the trial.

#### **3.8.3.4 Procedures to Encourage Continued Trial Participation**

In all cases of impending IMP discontinuation or consent withdrawal, investigators or subinvestigators will be given instructions to meet and discuss with the subject their options of continuing in the trial, preferably on therapy. The investigator or subinvestigator should ensure understanding and documentation of the reasons why the subject wishes to withdraw consent.

### **3.9 Screen Failures**

A screen failure subject is one from whom informed consent is obtained and is documented in writing (ie, subject has signed an ICF), but who is not enrolled in the treatment period of the trial. For screen failures, the following information will be recorded in the source documents and the CRF.

- Date of visit
- Date of informed consent
- Subject demographics
  - Date of investigation
  - Date of birth
  - Sex
  - Race
  - Ethnicity
  - Country where trial is performed
- Results of eligibility criteria assessment
- Date of assessment as screen failure
- Reason for screen failure

New subjects who participate in this trial but who are categorized as screening failures are permitted to be rescreened. Prior to rescreening, if performed, informed consent must be newly obtained and a new subject ID must be assigned.

### **3.10 Definition of Completed Subjects**

The treatment period is defined as the time period during which subjects are evaluated for safety and efficacy irrespective of whether the subject actually received all doses of the IMP. Subjects who are evaluated at the last scheduled visit during the treatment period will be defined as trial completers. For the purposes of this trial, subjects who are evaluated at Week 52 of the treatment period will be defined as trial completers.

### **3.11 Definition of Subjects Lost to Follow-up**

Subjects who cannot be contacted on or before the examinations at Week 52 of the treatment period, who do not have a known reason for discontinuation (eg, withdrew consent or AE), and for whom a survival status at the end of the trial cannot be determined will be classified as “lost to follow-up.” Subjects who did not undergo post-treatment observation will also be classified as “lost to follow-up.” Survival status can be determined from a variety of sources, either by obtaining acceptable documentation for death (ie, death certificate, medical records, public records, statement by a family member or primary care physician) or acceptable documentation for life (ie, direct contact with the subject, medical records, successful telephone contact with the subject, statement by a family member or primary care physician, or public records).

The investigator, subinvestigator, or designee will make 3 documented attempts to contact the subject by telephone and in the event the site is unable to reach the subject by telephone, the site will attempt to contact the subject via certified mail or an alternative similar method where appropriate, before assigning a “lost to follow-up” status, and will make a record of the inability to contact the subject, recording the dates of the 3 attempts at contact and the method(s) of contact in the source documents and the date and method of the last attempt at contact in the CRF.

### **3.12 Subject Compliance**

The investigator or subinvestigator will give subjects the following instructions to ensure their compliance with the protocol.

- 1) Site visits are to be made on the scheduled visit days as specified in the protocol (see [Section 3.7.1.6](#)).
- 2) No prohibited concomitant drugs are to be taken during the period from informed consent to Week 52 of the treatment period (or discontinuation).
- 3) No commercially available brexpiprazole is to be taken during the period from the assessment at Week 52 of the treatment period (or discontinuation) to the end of the post-treatment observation period.

- 4) The requirements regarding the method, duration, and frequency of administration of a commercially available antidepressant and the IMP are to be complied with (see [Section 3.2](#)). If the IMP compliance during the interval between 2 consecutive scheduled visits is less than 65%, the subject will be withdrawn from the trial (see [Section 3.8.3](#)).
- 5) Subjects must take appropriate contraceptive measures as instructed (see [Section 5.5](#)).

### **3.13 Protocol Deviations**

In the event of a significant deviation from the protocol due to an emergency, accident, or mistake (eg, violation of informed consent process, IMP dispensing or subject dosing error, treatment assignment error, subject enrolled in violation of eligibility criteria or concomitant therapy criteria), the investigator, subinvestigator, or designee will contact the sponsor at the earliest possible time by telephone. The investigator or subinvestigator and sponsor will come as quickly as possible to a joint decision regarding the subject's continuation in the trial. This decision will be documented by the investigator or subinvestigator and the sponsor, and reviewed by the site monitor. For major deviations, the date on which the deviation occurred and the details of the deviation will be recorded in the source documents and the CRF.

## **4 Restrictions**

### **4.1 Prohibited Concomitant Medications**

For appropriate assessment of the efficacy and safety of brexpiprazole, use of the drugs shown below is prohibited. However, in cases where rollover subjects have been using such drugs after Week 6 of the double-blind period (Phase B) of the double-blind trial (331-102-00058) or new subjects are using them during the screening period of this trial at the discretion of the investigator or subinvestigator, their dose should be gradually reduced and then discontinued by the following prohibition period:

- From 1 week prior to commencement of the treatment period through the end of the treatment period
  - Benzodiazepines (excluding ultrashort-acting sedative-hypnotic drugs)  
\*Necessary washout period: 7 days
- From 2 weeks prior to commencement of the treatment period through the end of the treatment period
  - MAO inhibitors  
\*Necessary washout period: 14 days
- From 24 hours before commencement of the treatment period through the end of the treatment period

- Central nervous system drugs (excluding ultrashort-acting sedative-hypnotic drugs, anticholinergic drugs for Parkinson's disease, antipyretic analgesic anti-inflammatory drugs, and general cold drugs)  
Note: Caution should be exercised to avoid concomitant use of CYP2D6 inhibitors, CYP3A4 inhibitors, and CYP3A4 inducers specified in Section 4.4 Other Restrictions (eg, chlorpheniramine, diphenhydramine, clemastine, and celecoxib).
- Chinese medicine (drugs indicated for neurosis, anxiety neurosis, neurasthenia, insomnia, and other disorders)
- Over-the-counter drugs used as hypnotics
- Supplements used for improvement of depressive symptoms (St. John's wort, S-adenosylmethionine [SAM-e],  $\omega$ -3 fatty acids, Kava extracts, and gamma-aminobutyric acid [GABA])
- Varenicline
- Adrenaline
- Drugs not approved in Japan
- During the post-treatment observation period
  - Commercially available brexpiprazole

## 4.2 Prohibited Concomitant Therapies

For appropriate assessment of the efficacy and safety of brexpiprazole, the following therapies are prohibited during the treatment period.

- Somatic therapy (electroconvulsive therapy, high-intensity phototherapy, sleep deprivation, transcranial magnetic stimulation)
- Psychotherapy (excluding supportive psychotherapies used in general clinical practice)

## 4.3 Restricted Concomitant Drugs

The use of the following drugs is restricted during the treatment period.

- Ultrashort-acting sedative-hypnotic drugs  
Ultrashort-acting sedative-hypnotic drugs that can be used in this trial are restricted to zolpidem, zopiclone, eszopiclone, and triazolam. The concomitant use of only one of the aforementioned drugs is allowed during the treatment period; 2 or more drugs are not to be coadministered simultaneously. Change in the types of the aforementioned drugs is allowed.
- Anticholinergic drugs for Parkinson's disease  
Anticholinergic drugs for Parkinson's disease, for which concomitant use during the treatment period is allowed, are biperiden, trihexyphenidyl, profenamine, piroheptine,

and mazaticol. In the case where extrapyramidal symptoms occur and use is necessary in the opinion of the investigator or subinvestigator, only one drug can be coadministered with no prophylactic use allowed. Change in the types of the aforementioned drugs is allowed.

- Antipyretic analgesic anti-inflammatory drugs, antihistamines  
Concomitant use is allowed if subjects were already using the drugs at the time of informed consent to treat complications; however, no changes in dose and regimen are allowed unless AEs occur or the use of these drugs is considered unnecessary because of remission of symptoms. Furthermore, short-term concomitant use, including use as a medication for colds during the treatment period, is also allowed. The topical external use of these drugs is allowed.  
Note: Caution should be exercised to avoid concomitant use of CYP2D6 inhibitors, CYP3A4 inhibitors, and CYP3A4 inducers specified in Section 4.4 Other Restrictions (eg, chlorpheniramine, diphenhydramine, clemastine, and celecoxib).
- $\beta$ -Blockers  
During the treatment period, use is allowed only for treatment of cardiovascular diseases, with no changes in the dose and regimen employed at the time of informed consent. The topical external use of these drugs is allowed.

#### 4.4 Other Restrictions

CYP2D6 inhibitors, CYP3A4 inhibitors and inducers, food products containing St. John's wort, and grapefruit, star fruit, Seville orange, and their juice and other processed products are likely to affect the pharmacokinetics of brexpiprazole and potentiate or reduce its effects. Caution should be exercised to avoid the consumption of these drugs and foods.

- CYP2D6 inhibitors (excluding topical agents in the dosage forms permitted for concomitant use as specified in Appendix 2):

Drug category	Nonproprietary name
Antihistamines	clemastine, chlorpheniramine, diphenhydramine
Antiallergic minor tranquilizers	hydroxyzine
Antiinflammatory agents	celecoxib
Analgesics	methadone
Antifungal agents	terbinafine
Antiarrhythmic agents	quinidine
Acid suppressants	cimetidine
Overactive bladder treatments	mirabegron
Antidepressants	clomipramine
Hyperthyroidism treatments	cinacalcet
Erythematosis treatments	hydroxychloroquine

- CYP3A4 inhibitors (excluding topical agents in the dosage forms permitted for concomitant use as specified in Appendix 2):

Drug category	Nonproprietary name
Antibiotics	erythromycin, quinupristin/dalfopristin (injection), clarithromycin, chloramphenicol, ciprofloxacin
Antifungal agents	itraconazole, clotrimazole, fluconazole, voriconazole
Calcium antagonists	diltiazem, verapamil
Antiarrhythmic agents	amiodarone
Acid suppressants	cimetidine
Antiemetics	aprepitant
Antineoplastic agents	imatinib, crizotinib
Immunosuppressants	ciclosporin
Anti-HIV agents	atazanavir, indinavir, cobicistat (combination), saquinavir, nelfinavir, fosamprenavir, ritonavir, lopinavir/ritonavir (combination)
Hepatitis C treatments	telaprevir, ombitasvir/paritaprevir/ritonavir (combination)

- CYP3A4 inducers (excluding topical agents in the dosage forms permitted for concomitant use as specified in Appendix 2):

Drug category	Nonproprietary name
Corticosteroids	cortisone, dexamethasone, triamcinolone, hydrocortisone, fludrocortisone, prednisolone, betamethasone, methylprednisolone
Antihormones	enzalutamide, mitotane
Cervical ripening agents	prasterone
Central nervous system stimulants	modafinil
Antiepileptics	oxcarbazepine, carbamazepine, phenytoin, fosphenytoin, phenobarbital, primidone
Pulmonary hypertension treatments	bosentan
Antituberculous agents	rifampicin (rifampin)
Anti-HIV agents	etravirine, efavirenz, nevirapine

- Foods and beverages: Food products containing St. John's wort, and grapefruit, star fruit, Seville orange, and their juice and other processed products

## 5 Reporting of Adverse Events

### 5.1 Definitions

An AE is defined as any untoward medical occurrence in a patient or clinical trial subject administered a medicinal product and which does not necessarily have a causal relationship with this treatment. Adverse events would not include information recorded as complications at screening (for new subjects) or baseline (for rollover subjects) for preplanned procedures for which the underlying condition was known and no worsening occurred. For rollover subjects, AEs that occurred during the double-blind trial (331-102-00058) and persist without recovery or resolution, but have not become exacerbated, will not be counted as AEs occurring in this trial. An adverse drug reaction is any untoward and unintended response to an IMP related to any dose administered.

A suspected adverse reaction is any AE for which there is a reasonable possibility that the IMP caused the AE.

An SAE includes any event that results in any of the following outcomes:

- Death
- Life-threatening; ie, the subject was, in the opinion of the investigator, or subinvestigator at immediate risk of death from the event as it occurred. It does not include an event that, had it occurred in a more severe form, might have caused death.
- Persistent or significant incapacity/disability or substantial disruption of the ability to conduct normal life functions.
- Requires inpatient hospitalization or prolongs hospitalization
  - Hospitalization itself should not be reported as an SAE; whenever possible the reason for the hospitalization should be reported.
  - Hospitalizations or prolonged hospitalizations for social admissions (ie, those required for reasons of convenience or other nonmedical need) are not considered SAEs.
- Congenital anomaly/birth defect.
- Other medically significant events that, based upon appropriate medical judgment, may jeopardize the subject and may require medical or surgical intervention to prevent one of the outcomes listed above, eg, allergic bronchospasm requiring intensive treatment in an emergency room or home, blood dyscrasias or convulsions that do not result in hospitalization, or the development of drug dependency or drug abuse.

Nonserious AEs are all AEs that do not meet the criteria for a “serious” AE.

Immediately Reportable Event (IRE):

- Any SAE
- Any AE related to occupational exposure.
- Potential drug-induced liver injury (DILI) (see [Section 5.4](#)).
- Pregnancies are also defined as IREs. Although normal pregnancy is not an AE, it will mandate IMP discontinuation and must be reported on an IRE form to the sponsor. Pregnancy will only be recorded in the source documents and the AE Section of the CRF if there is an abnormality or complication. This applies both to pregnancies of subjects and pregnancies of subjects' partners.

Clinical Laboratory Assessment Value Changes: It is the investigator's or subinvestigator's responsibility to review the results of all laboratory tests as they become available. This review will be documented by the investigator's or subinvestigator's dated signature on the laboratory report. For each abnormal laboratory test result, the investigator or subinvestigator needs to verify whether this is an abnormal (ie, clinically relevant) change from baseline for that individual subject. This determination, however, does not necessarily need to be made the first time an abnormal value is observed. The investigator or subinvestigator may repeat the laboratory test or request additional tests to verify the results of the original laboratory tests. If this laboratory value is considered medically relevant by the investigator or subinvestigator (subject is symptomatic, requiring corrective treatment or further evaluation), or if the laboratory value leads to discontinuation or meets the criteria for an SAE, this is considered an AE.

Severity: Adverse events will be graded on a 3-point scale and reported. The intensity of an AE is defined as follows:

**1 = Mild:** Discomfort noticed, but no disruption to daily activity.

**2 = Moderate:** Discomfort sufficient to reduce or affect normal daily activity.

**3 = Severe:** Inability to work or perform normal daily activity.

IMP Causality: Assessment of causal relationship between an AE and the IMP:

**Related:** There is a reasonable possibility of a temporal and causal relationship between the IMP and the AE.

**Not related:** There is no temporal or reasonable relationship between the IMP and the AE.

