#### **1.2.2.2 Confirmatory Trial in Subjects With Major Depressive Disorder (331-10-228)**

A double-blind, placebo-controlled trial was conducted outside Japan to evaluate the efficacy, safety, and tolerability of a fixed dose of brexpiprazole in subjects with major depressive disorder who had an insufficient response to antidepressant therapy. The trial was designed similarly to Trial 331-10-227 and had 2 treatment groups consisting of a

placebo group and a brexpiprazole 2-mg group. The change from baseline to Week 6 in the MADRS total score, the primary endpoint, showed significant improvement in the 2-mg group compared with the placebo group (LSMD:  $-3.12$ ,  $p = 0.0001$ ). In the efficacy data from a subgroup meeting the inclusion criteria revised during the trial, the change from baseline to Week 6 in the MADRS total score showed improvement in the 2-mg group compared with the placebo group (LSMD:  $-3.21$ ,  $p = 0.0002$ ).

The incidence of AEs was 59.0% in the brexpiprazole 2-mg group and 46.6% in the placebo group. The AEs reported in the brexpiprazole 2-mg group at an incidence of  $\geq 5\%$  and at more than double the incidence in the placebo group were weight increased (8.0% in the 2-mg group and 3.1% in the placebo group; hereinafter, the same order shall apply) and akathisia (7.4%, 1.0%). Most AEs in the brexpiprazole group or the placebo group were mild or moderate in severity. The incidence of SAEs was 1.1% in the 2-mg group and 1.0% in the placebo group. The incidence of AEs leading to discontinuation was 3.2% in the 2-mg group and 0.0% in the placebo group. The incidences of both SAEs and AEs leading to discontinuation were low in the brexpiprazole group as in the placebo group. No marked changes were noted in laboratory test values, vital signs, or ECGs in the brexpiprazole group.

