## 5.2 Eliciting and Reporting Adverse Events

The investigator or subinvestigator will periodically assess subjects for the occurrence of AEs. To avoid bias in eliciting AEs, subjects should be asked the nonleading question: “How have you felt since your last visit?” For all AEs (serious and nonserious) reported by the subject, the event name, start and stop dates, severity, seriousness, relationship to IMP, actions taken regarding IMP administration, and outcome thereof must be recorded in the source documents and CRFs provided by the sponsor. Adverse event and SAE collection is to begin after a subject has signed the ICF.

Use medical terminology in AE reporting. Adverse events should be reported as a single unifying diagnosis whenever possible or, in the absence of a unifying diagnosis, as individual signs or symptoms. Exacerbation or disease progression should be reported as an AE only if there are unusual or severe clinical features that were not present, or experienced earlier, or not expected based on the course of the condition. If a reported AE has worsened in severity or seriousness, it should be reported as a new AE on the CRF.

In addition, the sponsor must be notified immediately by e-mail, in principle, of any IREs according to the procedure outlined below, in [Section 5.3](#) Immediately Reportable Events. Special attention should be paid to recording hospitalization and concomitant medications.

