10.2 Adverse Events

All adverse events (AEs) will be coded by Medical Dictionary for Regulatory Activities (MedDRA) (Ver. 24.0) System Organ Class (SOC) and Preferred Term (PT). Numbers and proportions of subjects with the following AEs will be summarized by SOC and PT. If an AE occurs more than once in the same subject, the severest event will be used in summarization.

- Adverse events occurring after initiation of IMP administration (treatment-emergent adverse events [TEAEs])
- TEAEs by severity
- TEAEs with an outcome of death
- Serious TEAEs
- TEAEs leading to discontinuation of the IMP
- TEAEs occurring in $\geq 2\%$ of subjects in any group
- TEAEs by date of initial onset (1-7, 8-14, 15-28, 29-56, 57-84, 85-112, 113-140, 141-168, 169-196, 197-224, 225-252, 253-280, 281-308, 309-336, 337-364, > 364 , post-trial treatment)

TEAEs potentially causally related to the IMP will also be summarized in the same manner.

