- CT-7.2 Extent of Exposure to ADT (Safety Analysis Set)
- CT-7.3 Summary of Treatment Compliance (Efficacy Analysis Set)
- CT-8.1 Adverse Events (All Causalities) (Safety Analysis Set)
- CT-8.2.1 Incidence of TEAEs by MedDRA System Organ Class and Preferred Term (Safety Analysis Set)
- CT-8.2.2 Incidence of Drug-related TEAEs by MedDRA System Organ Class and Preferred Term (Safety Analysis Set)
- CT-8.3.1 Incidence of TEAEs by MedDRA System Organ Class, Preferred Term and Severity (Safety Analysis Set)
- CT-8.3.2 Incidence of Drug-related TEAEs by MedDRA System Organ Class, Preferred Term and Severity (Safety Analysis Set)
- CT-8.4.1 Incidence of Deaths due to TEAEs by MedDRA System Organ Class and Preferred Term (Safety Analysis Set)
- CT-8.4.2 Incidence of Deaths due to Drug-related TEAEs by MedDRA System Organ Class and Preferred Term (Safety Analysis Set)
- CT-8.5.1 Incidence of Serious TEAEs by MedDRA System Organ Class and Preferred Term (Safety Analysis Set)
- CT-8.5.2 Incidence of Serious Drug-related TEAEs by MedDRA System Organ Class and Preferred Term (Safety Analysis Set)
- CT-8.6.1 Incidence of TEAEs Resulting in Discontinuation of IMP by MedDRA System Organ Class and Preferred Term (Safety Analysis Set)
- CT-8.6.2 Incidence of Drug-related TEAEs Resulting in Discontinuation From Study by MedDRA System Organ Class and Preferred Term (Safety Analysis Set)
- CT-8.7.1 Incidence of TEAEs of at Least 2% in Any Group by MedDRA System Organ Class and Preferred Term (Safety Analysis Set)
- CT-8.7.2 Incidence of Drug-related TEAEs of at Least 2% in Any Group by MedDRA System Organ Class and Preferred Term (Safety Analysis Set)
- CT-8.8.1 Incidence of TEAEs by MedDRA System Organ Class, Preferred Term and Time to First Onset (Safety Analysis Set)
- CT-8.8.2 Incidence of Drug-related TEAEs by MedDRA System Organ Class, Preferred Term and

	Time to First Onset (Safety Analysis Set)
CT-8.9.1	Incidence of TEAEs for EPS (Safety Analysis Set)
CT-8.9.2	Incidence of TEAEs for Neuroleptic Malignant Syndrome (Safety Analysis Set)
CT-8.9.3	Incidence of TEAEs for Rhabdomyolysis and CPK Elevation (Safety Analysis Set)
CT-8.9.4	Incidence of TEAEs for Seizures (Safety Analysis Set)
CT-8.9.5	Incidence of TEAEs for Orthostatic Hypotension, Dizziness, and Syncope (Safety Analysis Set)
CT-8.9.6	Incidence of TEAEs for Suicidality (Safety Analysis Set)
CT-8.9.7	Incidence of TEAEs for Somnolence (Safety Analysis Set)

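### A rollover who stops brexpiprazole for an unworsened AE carried over from 331-102-00058 is absent from the TEAE discontinuation tables, and no rule reconciles those tables with the reasons for discontinuation

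*Protocol*

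**What the plan says.** **Counting rule.** Protocol 5.1 (Definitions) provides that rollovers' AEs that started in 331-102-00058 and "persist without recovery or resolution, but have not become exacerbated, will not be counted as AEs occurring in this trial". Nothing is said about such an AE when it is the reason for stopping the IMP.

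**Route back in.** Protocol 5.2: "If a reported AE has worsened in severity or seriousness, it should be reported as a new AE on the CRF". For laboratory results, Protocol 5.1 adds that "if the laboratory value leads to discontinuation or meets the criteria for an SAE, this is considered an AE".

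**Reason for withdrawal.** Protocol 3.8.3.2 has one main reason recorded in the CRF for each withdrawn subject. Its first category, 'Adverse event', includes item 1)e): "Subject decides to discontinue because of annoyance or discomfort due to a nonserious AE". The category does not require the event to be new or treatment-emergent.

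**Analyses.** SAP 10.2 lists "TEAEs leading to discontinuation of the IMP" and the corresponding drug-related summary, and takes TEAEs to be AEs arising after the IMP is started. Appendix 5 implements these as CT-8.6.1 and CT-8.6.2. Separately, SAP 7.1 summarises discontinuations by reason (CT-2.1 and CT-2.2), and Appendix 6 lists them (DREAS-1 and PDATA-3). SAP section 5 presents rollovers by Phase B assignment. SAP section 15 (Changes in the Planned Analyses) does not mention carried-over AEs.

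**The concern.** The trial's objective is long-term safety and efficacy, and AE discontinuation by preferred term is one of the main tolerability outputs. Consider a rollover who enters with mild akathisia from Phase B, tolerates it at the same grade for some months, and then gives up treatment because of it. This is a tolerability failure on brexpiprazole. The Introduction and section 2.1 of the protocol name akathisia as a problem with the existing augmentation drug. Yet the event is not a TEAE of this trial, so the tables that attribute discontinuations to preferred terms do not contain it.

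The error runs in one direction. It can only lower the AE discontinuation rate, and only in rollovers, because new subjects have no parent trial to carry an AE from.

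**Working it through.** The plan states no figure on this point, so the check is a trace of the rules through to the outputs, followed by what the documents allow on direction and size.

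**1. Is the event an AE of this trial?** Protocol 5.1 says it is not counted while unexacerbated. Protocol 5.2 makes it a new AE only if severity or seriousness worsens. Severity has three grades, defined by effect on daily activity, so a symptom can exhaust a subject's tolerance without changing grade. An AE that resolves in the gap of up to 28 days between Week 6 of Phase B and the start of treatment, and then recurs, is not persisting and is not lost.

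**2. Is it a TEAE?** Its onset precedes the first dose in this trial, and 5.1 removes it from the count in any case.

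**3. Which outputs show the discontinuation?**

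| Output | Built on | Subject present? |
|---|---|---|
| CT-8.6.1, CT-8.6.2 | TEAEs ending treatment | No |
| CT-9.3 | Title refers to AEs, not TEAEs | Undetermined: it needs an AE record showing the IMP withdrawn, and nothing tells the site to create one |
| CT-2.1, CT-2.2 | Main reason on the CRF | Yes, as a reason category; 'Adverse event' if so coded |
| DREAS-1, PDATA-3 | Main reason on the CRF | Yes, on the same terms |

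**4. Does CT-2.1 fill the gap?** Not fully. It reports reason categories, not preferred terms. In 3.8.3.2, 'Adverse event' also covers death, exacerbation of the underlying disease, manic switch and suicide risk. A reader comparing its 'Adverse event' row with CT-8.6.1 could find a difference that the plan does not explain.

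**5. Laboratory values.** The 5.1 clause on laboratory values that lead to discontinuation would make the event an AE, while the carry-over rule in the same section would leave it uncounted. The protocol does not say which prevails for a carried-over laboratory abnormality.

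**6. Direction.** Protocol 1.2.2.2 (331-10-228) gives six-week incidences of akathisia of 7.4% on 2 mg and 1.0% on placebo, and of weight increased of 8.0% and 3.1%. With no overlap between the two events:

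- brexpiprazole: 7.4 + 8.0 = 15.4 per 100
- placebo: 1.0 + 3.1 = 4.1 per 100

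If the Japanese double-blind trial is similar, carry-over of these two events would fall mainly on the prior-brexpiprazole column. Placebo rollovers can also carry AEs over.

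**7. Size.** This needs the number of rollovers, the number entering with an ongoing AE, the share of those AEs that persist, and the share that end treatment unworsened. The documents give none of these. Pure assumptions applied to the 15.4 per 100 show how far the answer can move:

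- half persist, and 10% to 30% of those stop: 15.4 × 0.5 × 0.10 = 0.77 to 15.4 × 0.5 × 0.30 = 2.31 per 100
- 10% persist, and 5% of those stop: 15.4 × 0.10 × 0.05 = 0.08 per 100

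The range is roughly thirtyfold and is set entirely by the assumptions.

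**The case against.** The strongest reply is that no discontinuation is lost. The withdrawal reason is its own CRF item, its 'Adverse event' category does not depend on TEAE status, and the subject is counted in CT-2.1. Section 5.1 says such AEs are not counted, which is not the same as not recorded. Section 5.2 asks for the action taken on the IMP for every AE the subject reports, and 3.8.3.2 requires follow-up of any AE that stops the IMP. A symptom that goes from tolerated to treatment-ending will often be graded worse and so become a new AE. Weight that keeps rising is an exacerbation. Akathisia is also measured by DIEPSS at every treatment visit and at discontinuation, and by BARS at discontinuation. The trial is uncontrolled and descriptive, and rollovers are already selected as Phase B completers.

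Much of this stands. A reader might infer that the subject vanishes from every output on AE discontinuation, or that a carried-over AE can never count. The documents do not support either inference: the reason tables and listings remain, CT-9.3 is open, worsening reinstates the AE, and the laboratory clause may do so too.

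A reader might also want to express the loss as a share of the 8.6% AE discontinuation rate in 331-10-238. That fails as well. The persistence and stopping rates have no source. The 331-10-228 incidences include subjects who left early and could not roll over. The 331-10-238 trial took subjects from earlier double-blind trials, and its own carry-over rule is not given. Its weight data (17.7% incidence, 2.0% stopping; 2.0 / 17.7 = 11%) also sit near the bottom of the 10% to 30% stopping range, and that 11% is not limited to unworsened cases.

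The reply does not remove the gap by preferred term. Scale scores do not attribute a discontinuation to akathisia and do not cover other AEs. The possibility that sites record the event anyway is not a rule that they must.

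**Conclusion.** The point holds in a limited form. Applied as written, Protocol 5.1 and SAP 10.2 leave a rollover who stops the IMP for an unworsened carried-over AE out of CT-8.6.1 and CT-8.6.2, and possibly out of CT-9.3. The discontinuation remains visible by reason category in CT-2.1, CT-2.2, DREAS-1 and PDATA-3, and sits under 'Adverse event' if the site codes it that way. No section tells sites how to code this case.

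The undercount is one-directional and confined to rollovers. That it falls mainly on prior-brexpiprazole subjects is probable, on the assumption that Phase B resembled 331-10-228. Its size cannot be calculated from the documents and may be small. This is a cheap improvement to safety reporting, not a flaw that threatens the trial's conclusions.

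**What to change.** 1. **Protocol 5.1 or CRF guidance.** Keep the rule that a carried-over, unworsened AE is not a new TEAE. Add that if it leads to discontinuation of the IMP, it is entered on this trial's AE page with its original onset date and the action 'IMP withdrawn'. State whether the carry-over rule or the laboratory clause governs a carried-over laboratory abnormality.
2. **SAP 10.2 and Appendix 5.** Show these subjects in a separate row of CT-8.6.1 and CT-8.6.2, labelled 'AE ongoing from 331-102-00058', and include them in CT-9.3, by Phase B assignment. Reconcile the result with the 'Adverse event' row of CT-2.1.
3. **If the CRF can no longer change.** SAP version 2.0 is dated 19 Jul 2022 and the synopsis ends the trial on 31 Jul 2022, so this may be the practical route. List, by Phase B assignment, the subjects whose reason is 'Adverse event' but who have no TEAE with the IMP withdrawn. Rollovers keep their subject ID from the double-blind trial, so their ongoing AEs should be traceable there.

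The cost is a sentence or two of guidance, one extra row in two tables, and one reconciliation. The downside is that the AE discontinuation rate shown for rollovers may look slightly less favourable.
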